#### 3.2 Background

07WYDZ

Refer to the Investigator's Brochure (IB)/approved labeling for detailed background information on navarixin and the MK-3475 IB/approved labeling for detailed background information on pembrolizumab.

04W5XD Confidential

#### 3.2.1 Pharmaceutical and Therapeutic Background

Navarixin is a CXCR2 antagonist.

### 3.2.1.1 Navarixin Pharmaceutical and Therapeutic Background

The ELRCXC chemokine-CXCR1/2 axis mediates pleiotropic effects that impact tumorigenesis: 1) promotion of tumor resistance by enhancing the immunosuppressive tumor microenvironment (TME) by recruitment of neutrophils/myeloid-derived suppressor cells (MDSCs), 2) promotion of angiogenic responses, and 3) activation of epithelial-mesenchyme transition (EMT), which is associated with metastasis and stemness [David JM, Dominguez C, Hamilton DH, Palena C. 2016] [Acharyya S, Oskarsson T, Vanharanta S, Malladi S, Kim J 2012] [Condamine T, Ramachandran I, Youn JI, Gabrilovich DI. 2015].

CXCR2 antagonists function to inhibit the translocation of granulocytes (including neutrophils) out of the marrow and into circulation (and, inhibit translocation of MDSCs into tumors) [Highfill SL, Cui Y, Giles AJ, Smith JP, Zhang H, Morse E 2014]. As expected, the class of CXCR2 antagonists demonstrates a mechanism-based decrease in circulating neutrophils. Therefore, the neutrophil count serves as an easily monitorable functional biomarker assay. Navarixin clinical trials have demonstrated a dose-dependent decrease in neutrophils, suggesting the molecule is sufficient to test the hypothesis: CXCR2 antagonism, in combination with pembrolizumab, improves outcomes for cancer patients relative to pembrolizumab alone.

MDSCs are present and active in a number of different tumor types [David JM, Dominguez C, Hamilton DH, Palena C. 2016] [Kumar V, Patel S, Tcyganov E, Gabrilovich DI. 2016]. Likewise, CXCR2 is expressed in a diverse set of tumors. Recent data suggest that CXCR2 antagonism might reverse tumor immune suppression caused by MDSCs [Highfill SL, Cui Y, Giles AJ, Smith JP, Zhang H, Morse E 2014] [Theiyanthiran B, DeVito NC 2017]. In addition, antagonism of CXCR2 has been shown to inhibit tumor metastasis and neoangiogenesis in preclinical models. CXCR2 inhibition in combination with immunotherapy shows enhanced anti-tumor activity (anti-PD-1/anti-CTLA-4) in a preclinical prostate model [Lu X, Horner JW, Paul E, Shang X, Troncoso P, Deng P 2017]. CXCR2 inhibition enhances T cell entry, suppresses metastases, and confers sensitivity to anti-PD-1 treatment in KPC PDAC model. In addition, disruption of CXCR2-mediated MDSC tumor trafficking enhances anti-PD-1 efficacy in a syngeneic RMS tumor models. Moreover, data indicates that navarixin treatment can enhance the anti-tumor activity of PD-1 blockade in a B16-F10 syngeneic tumor model that shows modest activity to anti-PD-1 as a monotherapy (complete responses observed in the combination arm).

No studies with navarixin have been initiated in oncology indications. However, it was previously developed by Schering for non-oncology indications (chronic obstructive pulmonary disease [COPD], asthma, psoriasis). As a result of this development, over 900 subjects were treated with navarixin in clinical trials. Several Phase II studies were conducted in COPD, asthma, and psoriasis. No impact of treatment was observed in the psoriasis study. Two small asthma studies showed trends to clinically significant results.

04W5XD

The largest Phase II trial was a proof of concept (POC) study in patients with moderate to severe COPD in which navarixin 50 mg was compared with placebo. Navarixin treatment led to statistically significant improvement in forced expiratory volume (FEV) in patients with COPD who were current smokers. Treatment discontinuations for Grade 2 neutropenia were observed. No increases in infections or fevers were observed in treated patients versus the placebo group. Navarixin development was discontinued due to the modest and restricted (current smokers) observed benefit.

Multiple Phase I studies in healthy volunteers confirm that navarixin induces a dose dependent peripheral reduction in neutrophils; 24% and 48% median ANC decrease for 30 and 100 mg respectively. Neutrophil migration from the marrow is inhibited, and no marrow hypo-cellularity was observed. The neutrophil reduction is rapidly reversible on dosing cessation, and peripheral neutrophils return to baseline values in 48-96 hours without cytotoxic or myelosuppressive effects on the bone marrow.

Several CXCR2 antagonists are under development. AstraZeneca has reported AZD5069 Phase 1 results in combination with durvalumab [Steele CW, Karim SA, Leach JDG, Bailey P, Upstill-Goddard R 2016]. The combination is reported to be well-tolerated, and the AZD5069 combination with durvalumab does not appear to enhance toxicities observed from either AZD5069 or durvalumab monotherapies.

Navarixin development will focus on combinations with immune checkpoint inhibitors (pembrolizumab). The removal of the immune suppression induced by navarixin, combined with immune checkpoint abrogation, is hypothesized to improve cancer therapy outcomes relative to either treatment alone. The mechanistic, dose-dependent, rapidly reversible. decrease in peripheral neutrophils induced by navarixin (and all CXCR2 antagonists) will serve as a readily monitorable pharmacodynamic marker in this trial.

### 3.2.1.2 Pembrolizumab (MK-3475) Pharmaceutical and Therapeutic Background

KeytrudaTM (pembrolizumab) is indicated for the treatment of patients across a number of indications. For more details on specific indications, refer to the pembrolizumab IB.

#### 3.3 Benefit/Risk Assessment

It cannot be guaranteed that participants in clinical studies will directly benefit from treatment during participation, as clinical studies are designed to provide information about the safety and effectiveness of an investigational medicine.

Additional details regarding specific benefits and risks for participants participating in this clinical study may be found in the accompanying Investigators Brochure (IB) and Informed Consent documents.

32

**Product:** MK-7123 SCH 527123 **Protocol/Amendment No.:** 034-01

## 4. Objectives/Hypotheses and Endpoints

Male/female participants of at least 18 years of age with selected advanced/metastatic solid tumors will be enrolled in this study.

Objective	Endpoint						
Primary							
Objective: To evaluate the objective response rate (ORR) as assessed by the investigator based on Response Evaluation Criteria in Solid Tumors Version 1.1 (RECIST 1.1) following administration of navarixin in combination with pembrolizumab.	Objective response is a confirmed complete response (CR) or partial response (PR).						
Objective: To determine the safety and	Dose-limiting toxicity (DLT)						
tolerability of navarixin in combination with pembrolizumab.	Adverse event (AE)						
with perioronzumuo.	• Discontinuing study treatment due to an AE.						
Secondary							
Objective: To evaluate objective response rate (ORR) as assessed by investigator based on iRECIST (modified RECIST 1.1) [Seymour, L., et al 2017], progression-free survival (PFS) as assessed by investigator based on RECIST 1.1 and iRECIST, and overall survival (OS) following administration of navarixin in combination with pembrolizumab	
 
Objective response is a confirmed CR or PR.
 
PFS is time from the first dose of study medication to the first documented disease progression or death due to any cause, whichever occurs first.
 
OS is time from the first dose of study medication to death due to any cause.
 
						
Objective: To evaluate the pharmacodynamics as measured by absolute neutrophil counts (ANC) following administration of navarixin in combination with pembrolizumab.	• ANC in 10  /L						
Objective: To evaluate the pharmacokinetics (PK) of navarixin when administered in combination with pembrolizumab	PK parameters including area under the curve (AUC) in ng·hr/mL, maximum concentration (C max ) in ng/mL, trough concentration (C trough ) in ng/mL						

Objective	Endpoint						
Tertiary/Exploratory							
Objective: To evaluate the development of circulating antipembrolizumab antibodies, as appropriate, following administration of navarixin in combination with pembrolizumab	Anti- pembrolizumab antibody level						
Objective: To evaluate the relationship between navarixin PK and ANC	• ANC; navarixin PK parameters including AUC, C max , and C trough						
Objective: To identify molecular (genomic, metabolic and/or proteomic) biomarkers that may be indicative of clinical response/resistance, safety, pharmacodynamic activity, and/or the mechanism of action of navarixin in combination with pembrolizumab.	Germline genetic variation, genetic (deoxyribonucleic [DNA]) mutations from tumor, tumor and blood ribonucleic acid (RNA) variation, proteomics and immunohistochemistry (IHC), and other blood-derived biomarkers						

### 5. Study Design

#### 5.1 **Overall Design**

This is a stratified, parallel, 2-arm (2-dose), randomized, uncontrolled multicenter study of navarixin in combination with pembrolizumab in participants with selected advanced/metastatic solid tumors. The study will use a 2-stage adaptive design based on prespecified criteria. There is no untreated/placebo comparator arm.

Participants with PD-(L)1 refractory NSCLC, CRPC, or MSS CRC will be randomized into one of two dose arms. In dose Arm A, participants will be treated with 30 mg orally QD navarixin. In dose Arm B, participants will be treated with 100 mg orally QD navarixin. Participants in both Arms A and B will be treated concomitantly with pembrolizumab 200 mg IV O3W.

Per the interim safety analysis, if no more than 3 participants in the first 10 evaluable participants have experienced DLTs during the first cycle in an arm, this arm may be expanded by enrolling an additional 20 participants to complete Stage 1. However, during Stage 1, if at any time >3 DLTs are observed within the first 10 evaluable participants, enrollment into an arm will be discontinued.

In addition, the following stopping rule is included for excessive toxicity occurring outside the current defined DLT window. If 4 or more of the first 10 evaluable participants have a DLT per current protocol definition (either within the first cycle DLT observation window or outside this window) after they have all finished the first cycle observation, enrollment into the arm may be discontinued unless totality of the data (eg, including efficacy) supports a favorable risk-benefit trade-off.

Safety and tolerability will be continuously monitored throughout the study duration. If the regimen is deemed intolerable, the arm may be discontinued even if stopping rule is not met.

The overall design is an adaptive 2-stage design. In each arm, up to 30 participants will be enrolled in the first stage, and up to 30 participants in the second stage. In the first stage, 30 participants (with 10 per tumor type) will be enrolled in each arm (dose level). When all participants in a given arm with a given tumor type complete the first on-treatment scan at 9 weeks or when clinically indicated (see Section 9.2.1.2), a futility analysis will be conducted to determine whether that tumor type and arm will progress to Stage 2. If a tumor type passes the futility analysis (see Section 5.1.4) in Stage 1, at least 10 participants will be enrolled with that tumor type in the second stage.

Initial enrollment in each dose arm will be staggered. The first 3 participants in dose Arm A or dose Arm B will be enrolled no more frequently than 1 participant per week, to allow for peripheral neutrophil assessment between participants. Peripheral neutrophil assessment (ANC) will occur at baseline, Day 3, and Day 8 during the first cycle for all participants. Decreased ANC counts typically return to normal in 48-96 hours following dosing cessation. Standard support for oncology patients with low ANC will be considered as appropriate. See dose reduction algorithm (Section 7.2.1) for more information.

Specific procedures to be performed during the study, as well as their prescribed times and associated visit windows, are outlined in the Study SoA - Section 2. Details of each procedure are provided in Section 9 – Study Assessments and Procedures.

04W5XD

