## **5.1.3** Dose Limiting Toxicity

Formal DLT evaluation will be performed at the interim safety analysis, following completion of one cycle of treatment by 10 evaluable participants in each dose arm. DLT nonevaluable participants will not be replaced. For example, if one of the first 10 participants in an arm is nonevaluable for DLT, then the next DLT evaluable participant enrolled and treated in the arm will be included in the interim safety analysis. The DLT evaluation period will be for one cycle (Day 1 to Day 21. Day 1 is considered the date a study drug was first administered and not the date of randomization if dosing did not occur on the date of randomization). During this time, supportive treatment with G-CSF will not be allowed.

An arm dose will be considered intolerable if >3 of 10 evaluable participants experience DLTs in Cycle 1. If the arm dose is not tolerated at 30 mg (and 100 mg), the arm may be discontinued and the protocol may be amended to include a lower navarixin dose.

All toxicities will be graded based on investigator assessment (Appendix 4 "Assessment of Intensity").

The occurrence of any of the following toxicities during Cycle 1 will be considered a DLT, if assessed by the investigator to be possibly, probably, or definitely related to study treatment:

- 1) Grade 4 non-hematologic toxicity (not laboratory)
- 2) Grade 4 anemia of any duration
- 3) Grade 3 anemia lasting >7 days or requiring transfusion
- 4) Grade 4 hematologic toxicity (other than anemia) lasting ≥7 days, except thrombocytopenia
  - a) Grade 4 thrombocytopenia of any duration
  - b) Grade 3 thrombocytopenia associated with bleeding
- 5) Grade 3 non-hematologic toxicity (not laboratory) lasting >3 days despite optimal supportive care.
- 6) Any Grade 3 or Grade 4 non-hematologic laboratory value if:
  - Medical intervention is required to treat the participant, or
  - The abnormality leads to hospitalization, or
  - The abnormality persists for >72 hours.

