Safety Analyses	as appropriate (e.g. counts, percentages). Miettinen and Nurminen's method will be used to estimate the difference			
	between the 2 arms and its 95% confidence interval for			
	number of participants with a DLT, number of participants			
	with ≥1 AE and number of participants discontinuing study			
Intorim Analysas	treatment due to an AE.  An interim safety analysis is planned for each arm after the			
Interim Analyses	An interim safety analysis is planned for each arm after the first 10 participants across tumor types have finished at least			
	one cycle of therapy in a given arm. An interim futility			
	analysis is planned for each tumor type in each arm after the			
	first 10 participants in each tumor type have finished the first tumor assessment.			
	Additional interim analysis may be conducted to enable			
	future trial planning at the Sponsor's discretion and data will			
	be examined on a continuous basis to allow for timely			
	decisions.			

89

**Product:** MK-7123 SCH 527123 **Protocol/Amendment No.:** 034-01

Multiplicity	No multiplicity adjustment is planned in this Phase 2 trial.	
Sample Size and Power	1 0 0	

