#### 10.7 Interim Analyses

There is one planned interim safety analysis and one planned interim futility analysis in this trial.

An interim safety analysis is planned for each arm after the first 10 participants across tumor types have finished at least one cycle of therapy in a given arm. If no more than 3 participants in the first 10 participants have experienced DTLs during the first cycle in a given arm, this arm may be expanded by enrolling 20 additional participants to complete Stage 1. Otherwise, this arm may be terminated due to safety concern.

An interim futility analysis is planned for each tumor type in each arm after the first 10 participants in each tumor type have at least 1 post-baseline scan assessment. If 1 or more

responses (ie,  $\geq 10\%$  response rate) are observed in a tumor type within an arm, this tumor type may be expanded to enroll at least 10 additional participants in Stage 2. Otherwise, this tumor type may be stopped early for futility. If the true response rate is 16%, there is an 82% chance to continue the study at the futility evaluation. If the true response rate is 20%, there is an 89% chance to continue the study at the futility evaluation.

Additional interim analysis may be conducted to enable future trial planning at the Sponsor's discretion and data will be examined on a continuous basis to allow for timely decisions.

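### In 5.1, four or more of the first 10 evaluable participants with Cycle 1 DLTs is a mandatory enrollment stop under one rule and a waivable one under the next

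*Combined protocol and SAP*

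**What the plan says.** Section 5.1 allows an arm to expand by 20 participants to complete Stage 1 when no more than 3 of the first 10 evaluable participants have had a Cycle 1 DLT. It then gives two stopping rules.

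- **First rule.** During Stage 1, "if at any time >3 DLTs are observed within the first 10 evaluable participants, enrollment into an arm will be discontinued". No exception is stated.
- **Second rule.** Its stated purpose: "the following stopping rule is included for excessive toxicity occurring outside the current defined DLT window". Its trigger is 4 or more of the first 10 evaluable participants with a DLT, "either within the first cycle DLT observation window or outside this window", assessed once all of them have finished Cycle 1. Its consequence: "enrollment into the arm may be discontinued unless totality of the data (eg, including efficacy) supports a favorable risk-benefit trade-off".

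Two other sections address the Cycle 1 boundary. Section 5.1.3 treats a dose as intolerable when more than 3 of 10 evaluable participants have Cycle 1 DLTs, and then says that the arm may be discontinued and the protocol amended to a lower dose. Section 10.7 offers expansion under this condition: "If no more than 3 participants in the first 10 participants have experienced DTLs during the first cycle in a given arm". It continues: "Otherwise, this arm may be terminated due to safety concern".

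**The concern.** The two rules in 5.1 sit in consecutive paragraphs and share a threshold and a set of participants. For an arm with four or more Cycle 1 DLT participants, the first leaves no choice about enrollment. The second, read as written, leaves the choice open and names efficacy as a ground for continuing.

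The stakes are those of a primary safety endpoint. DLT is listed as one in Section 4, Section 3.2.1.1 says that no oncology study of navarixin had been initiated, and Section 7.4 makes the trial open-label to the sponsor. If the conflict arose, whoever decided would have text to support either course. A rule added to extend protection to late toxicity would then weaken the stop beside it.

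**Working it through.** **Inputs.** The two triggers and consequences are from 5.1, the DLT definition and window (Cycle 1, Day 1 to Day 21) from 5.1.3, and the interim wording from 10.7. The documents state no DLT rate and no operating characteristic for the DLT rule, so there is no figure of the plan's to reproduce here.

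**Step 1: overlap of the triggers.** Take all 10 evaluable participants as having finished Cycle 1. Let *a* be the number with a Cycle 1 DLT and *b* the number whose first qualifying toxicity came later. Because 5.1.3 defines a DLT as a Cycle 1 event, I read the first rule as applying to *a*. The second applies to *a* + *b*.

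| *a* | *b* | First rule (*a* > 3) | Second rule (*a* + *b* ≥ 4) |
|---|---|---|---|
| 3 | 0 | not met | not met |
| 3 | 1 | not met | met, waivable |
| 2 | 2 | not met | met, waivable |
| 4 | 0 | met, mandatory | met, waivable |
| 5 | 0 | met, mandatory | met, waivable |

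Every row with *a* ≥ 4 meets both. The first rule counts DLTs and the second counts participants, but this does not remove the overlap: four participants with a DLT are at least four DLTs, which is more than three.

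**Step 2: is precedence settled elsewhere?** Sections 5.1.3 and 10.7 both use permissive wording, and both speak of the arm rather than of enrollment. They neither repeat the mandatory enrollment stop nor give it priority.

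**Step 3: how often the boundary is reached.** With *X* binomial(10, *p*),

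P(*X* ≥ 4) = 1 − Σ C(10, *k*) *p*^*k* (1 − *p*)^(10 − *k*), *k* = 0 to 3.

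As a check that exact binomial is the plan's own approach, the futility figures in 10.7 follow from it: 1 − 0.84^10 = 0.825 and 1 − 0.80^10 = 0.893, against the stated 82% and 89%.

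For *p* = 0.20: 1 − (0.1074 + 0.2684 + 0.3020 + 0.2013) = 1 − 0.8791 = 0.1209. Across assumed rates:

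| Assumed Cycle 1 DLT rate | P(4 or more of 10) |
|---|---|
| 10% | 1.3% |
| 20% | 12.1% |
| 30% | 35.0% |
| 40% | 61.8% |

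These figures treat all 10 as observed. If the fourth DLT comes before 10 evaluable participants are enrolled, the first rule stops enrollment and the second rule's condition is not yet met. The figures are therefore an upper bound on how often both rules apply together.

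**The case against.** The strongest reply is that the rules work in sequence. The second is offered as an addition, is introduced for toxicity outside the window, and applies only after all 10 have completed Cycle 1. The first applies at any time, so an arm with four Cycle 1 DLTs would already have stopped enrolling. On this view the in-window wording is there so that mixed counts, such as three early and one late, can be added up. That is probably the intent, and the Amendment 01 summary also describes the second rule as covering toxicity outside the window. But the operative trigger does not exclude the case where Cycle 1 DLTs alone reach four, and a stopping rule should not depend on inferring that it does.

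Other safeguards exist. Section 5.1 allows an arm to be stopped even when no rule is met, and 5.3.1 provides for early termination on a health hazard. These are powers to stop; they do not restore a mandatory stop that another rule makes waivable.

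Figure 2 gives guidance on dose decision and expansion and may settle precedence. It is not visible here, so the finding is limited to the text.

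Three stronger readings are tempting, and the documents do not support them.

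- **That the plan permits the 20-participant expansion after four Cycle 1 DLTs.** Sections 5.1 and 10.7 offer expansion only at three or fewer, 5.1.3 calls the dose intolerable above that, and the waiver clause does not itself grant the expansion.
- **That 5.1.3 and 10.7 contradict the mandatory stop.** They concern discontinuing the arm, while the first rule concerns enrollment. This is misalignment, not contradiction.
- **That the SAP sections use a different denominator.** Section 10.1 sets the interim after the "first 10 participants across tumor types have finished at least" one cycle, and 10.7 likewise omits the word evaluable. But 5.1.3 says that if one of the first 10 is nonevaluable, "the next DLT evaluable participant enrolled and treated in the arm will be included in the interim safety analysis", and 10.5.2 defines the DLT evaluable population and refers back to 5.1.3.

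**Conclusion.** The concern holds as a conflict of wording within 5.1. When four or more of the first 10 evaluable participants have Cycle 1 DLTs and all 10 have finished Cycle 1, one rule requires enrollment into the arm to stop and the next makes the same stop waivable. The likely intent is clear; the text does not carry it.

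No stated number in the plan is wrong. The 12%, 35% and 62% rest on assumed DLT rates of 20%, 30% and 40% and on independent participants. A reader might take them as the chance of harm or of a waiver being used; they are neither. They do show that the boundary is seldom reached if the dose is well tolerated and often reached if it is toxic, which is when the rule needs to be unambiguous.

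**What to change.** 1. In 5.1, limit the second rule to cases where 4 or more of the first 10 evaluable participants *is reached only by counting DLTs outside the Cycle 1 window*, and state that the mandatory Cycle 1 enrollment stop takes precedence.
2. In 5.1.3 and 10.7, say that enrollment into the arm will be discontinued at more than 3 of 10 evaluable participants with Cycle 1 DLTs. Leave the handling of participants already on treatment, and any lower-dose amendment, discretionary.
3. Check Figure 2 against the revised text.
4. Optional: add the word evaluable in 10.1 and 10.7.
5. If the first rule is changed from a count of DLTs to a count of participants, record it as a deliberate clarification in line with 5.1.3. Taken literally, the present wording stops an arm when three participants contribute four DLTs; a participant count would not, so the change can make the stop later.

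The cost is wording in 5.1, 5.1.3 and 10.7, plus the figure check. The sponsor gives up only an override that the first rule already denies. Sample size, endpoints and analyses are untouched, and items 1 and 2 leave the first rule's threshold as it stands.

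The second rule keeps a real role. With an assumed Cycle 1 rate of 20% and a rate of 10% for later DLTs among those without one in Cycle 1, the combined rate is 0.20 + 0.80 × 0.10 = 0.28, and P(4 or more of 10) is 29.8%. Of that, 12.1 points come from Cycle 1 DLTs alone and 17.7 points (29.8 − 12.1) arise only by counting later ones.
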